## 7. ADVERSE EVENTS: LIST AND REPORTING REQUIREMENTS

[figure not shown]
Adverse event (AE) monitoring and reporting is a routine part of every clinical trial. The following list of reported and/or potential AEs (Section 7.1) and the characteristics of an observed AE (Section 7.2) will determine whether the event requires expedited reporting **in addition** to routine reporting.

[figure not shown]
### 7.1 Expected Toxicities

#### 7.1.1 Adverse Events List

##### 7.1.1.1 Adverse Event List(s) for Ulocuplumab

**Table 5.5.5.1-1:**

#### 7.1.1.2 Adverse Event List for Ibrutinib

##### Risks

##### Bleeding-related events

There have been reports of hemorrhagic events in subjects treated with ibrutinib both with and without thrombocytopenia. These include primarily minor hemorrhagic events such as contusion, epistaxis, and petechiae; and major hemorrhagic events, some fatal, including gastrointestinal bleeding, intracranial hemorrhage and hematuria. Use of ibrutinib in subjects requiring other anticoagulants or medications that inhibit platelet function may increase the risk of bleeding. Subjects with congenital bleeding diathesis have not been studied.

## **Cardiac**

Atrial fibrillation and atrial flutter have been reported in subjects treated with ibrutinib, particularly in subjects with cardiac risk factors, hypertension, acute infections, and a previous history of atrial fibrillation.

## **Cytopenias**

Treatment-emergent Grade 3 or 4 cytopenias (neutropenia, thrombocytopenia, and anemia) were reported in subjects treated with ibrutinib.

## **Diarrhea**

Diarrhea is the most frequently reported non-hematologic AE with ibrutinib monotherapy and combination therapy. Other frequently reported gastrointestinal events include nausea, vomiting, and constipation. These events are rarely severe. Should symptoms be severe or prolonged, follow the protocol dose modification guidelines (see Section 6).

## **Infections**

Fatal and non-fatal infections have occurred with ibrutinib therapy. At least 25% of subjects with MCL and 35% of subjects with CLL had Grade 3 or greater infections per NCI Common Terminology Criteria for Adverse Events (CTCAE). The most commonly reported infections include pneumonia, cellulitis, urinary tract infection and sepsis. Although causality has not been established, cases of progressive multifocal leukoencephalopathy (PML) have occurred in patients treated with ibrutinib.

## **Non-Melanoma Skin Cancer**

Non-melanoma skin cancers have occurred in patients treated with ibrutinib. Monitor patients for the appearance of non-melanoma skin cancer.

## **Rash**

Rash has been commonly reported in subjects treated with either single agent ibrutinib or in combination with chemotherapy. In a randomized Phase 3 study (PCYC-1112-CA), rash occurred at a higher rate in the ibrutinib arm than in the control arm. Most rashes were mild to moderate in severity.

## **Lymphocytosis and Leukostasis**

### **Leukostasis**

There were isolated cases of leukostasis reported in non-WM subjects treated with ibrutinib. A high number of circulating lymphocytes ( $>400,000/\mu\text{L}$ ) may confer increased risk.

### **Lymphocytosis**

Upon initiation of treatment, a reversible increase in lymphocyte counts (ie,  $\geq 50\%$  increase from baseline and an absolute count  $>5000/\mu\text{L}$ ), often associated with reduction of lymphadenopathy, has been observed in most subjects with CLL/ small lymphocytic lymphoma (SLL) treated with ibrutinib. This effect has also been observed in some subjects with MCL treated with ibrutinib. This observed lymphocytosis is a pharmacodynamic effect and should not be considered progressive disease in the absence of other clinical findings. In both disease types, lymphocytosis

typically occurs during the first few weeks of ibrutinib therapy (median time 1.1 weeks) and typically resolves within a median of 8.0 weeks in subjects with MCL and 18.7 weeks in subjects with CLL/SLL.

A large increase in the number of circulating lymphocytes (eg, >400,000/ $\mu$ l) has been observed in non-WM subjects. Lymphocytosis was uncommon in subjects with WM treated with ibrutinib, and was typically <5,000/ $\mu$ l.

### **Tumor Lysis Syndrome**

There have been reports of tumor lysis syndrome (TLS) events in non-WM subjects treated with single-agent ibrutinib or in combination with chemotherapy. Subjects at risk of tumor lysis syndrome are those with comorbidities and/or risk factors such as high tumor burden prior to treatment, increased uric acid (hyperuricemia), elevated lactate dehydrogenase (LDH), bulky disease at baseline, and preexisting kidney abnormalities.

### **Interstitial Lung Disease (ILD)**

Cases of interstitial lung disease (ILD) have been reported in patients treated with ibrutinib. Monitor patients for pulmonary symptoms indicative of ILD.

### **Other Malignancies**

All new malignant tumors including solid tumors, skin malignancies and hematologic malignancies will be reported for the duration of study treatment and during any protocol-specified follow-up periods including post-progression follow-up for overall survival. If observed, enter data in the corresponding eCRF.

## Treatment-Emergent Adverse Events in > 10% of Subjects

Treatment-emergent AEs in more than 10% of subjects receiving ibrutinib as monotherapy (N=1071) are summarized in [Table 5](#). The most frequently reported treatment-emergent AEs were diarrhea, fatigue, nausea, cough, anemia, pyrexia, and neutropenia.

**Table 5: Treatment-Emergent Adverse Events (any grade) in >10% of Subjects Receiving Ibrutinib Monotherapy including crossover patients (Safety Population)**

	Monotherapy Studies
Number of Subjects	1071
Subject with 1 or more events	987 (92.2%)
Preferred Term	
Diarrhoea	429 (40.1%)
Fatigue	315 (29.4%)
Nausea	238 (22.2%)
Cough	199 (18.6%)
Anaemia	188 (17.6%)
Pyrexia	185 (17.3%)
Neutropenia	178 (16.6%)
Arthralgia	159 (14.8%)
Oedema peripheral	159 (14.8%)
Constipation	158 (14.8%)
Thrombocytopenia	158 (14.8%)
Upper respiratory tract infection	147 (13.7%)
Muscle spasms	146 (13.6%)
Vomiting	142 (13.3%)
Dyspnoea	130 (12.1%)
Headache	127 (11.9%)
Pneumonia	127 (11.9%)
Decreased appetite	120 (11.2%)
Contusion	117 (10.9%)
Dizziness	108 (10.1%)

Note: Monotherapy studies includes PCYC-1102-CA, PCYC-1104-CA, PCYC-1106-CA, PCYC-1112-CA, PCYC-1117-CA, PCYC-1118E-CA, PCYC-04753, PCI-32765-JPN-101, PCI32765MCL2001, and PCI32765CLL3001(crossover only).

[TSFAE01B.RTF] [JNJ-54179060\Z\_IB\DBR\_IB\_2015\RE\_IB\_2015\PROD\TSFAE01B.SAS] 26JUN2015, 11:43

## 7.2 Adverse Event Characteristics

- **CTCAE term (AE description) and grade:** The descriptions and grading scales found in the revised NCI Common Terminology Criteria for Adverse Events (CTCAE) version 4.0 will be utilized for AE reporting. All appropriate treatment areas should have access to a copy of the CTCAE version 4.0. A copy of the CTCAE version 4.0 can be downloaded from the NCI web site [http://evs.nci.nih.gov/ftp1/CTCAE/CTCAE\\_4.03\\_2010-06-14\\_QuickReference\\_8.5x11.pdf](http://evs.nci.nih.gov/ftp1/CTCAE/CTCAE_4.03_2010-06-14_QuickReference_8.5x11.pdf)
- **For expedited reporting purposes only:**
  - AEs for the agent(s) that are listed above should be reported only if the adverse event varies in nature, intensity or frequency from the expected toxicity information which is provided.
  - Other AEs for the protocol that do not require expedited reporting are outlined in the next section (Expedited Adverse Event Reporting) under the sub-heading of Protocol-

### Specific Expedited Adverse Event Reporting Exclusions.

- **Attribution** of the AE:
  - Definite – The AE is *clearly related* to the study treatment.
  - Probable – The AE is *likely related* to the study treatment.
  - Possible – The AE *may be related* to the study treatment.
  - Unlikely – The AE is *doubtfully related* to the study treatment.
  - Unrelated – The AE is *clearly NOT related* to the study treatment.

## 7.3 Expedited Adverse Event Reporting

7.3.1 Investigators **must** report to the Overall PI any serious adverse event (SAE) that occurs after the initial dose of study treatment, during treatment, or within 30 days of the last dose of treatment on the local institutional SAE form.

### 7.3.2 DF/HCC Expedited Reporting Guidelines

Investigative sites within DF/HCC will report AEs directly to the DFCI Office for Human Research Studies (OHRS) per the DFCI IRB reporting policy.

### 7.3.3 Protocol-Specific Expedited Adverse Event Reporting Exclusions

For this protocol only, the AEs/grades listed below do not require expedited reporting to the Overall PI or the DFCI IRB. However, they still must be reported through the routine reporting mechanism (i.e. case report form).

CTCAE SOC	Adverse Event	Grade	Hospitalization/ Prolongation of Hospitalization	Attribution	Comments
Investigations	Platelet count decreased	4	No	Related	If hospitalization required, must be reported to DFCI IRB and PI
Investigations	Neutrophil count decreased	4	No	Related	If hospitalization required, must be reported to DFCI IRB and PI

## 7.4 Expedited Reporting to the Food and Drug Administration (FDA)

The Overall PI, as study sponsor, will be responsible for all communications with the FDA. The Overall PI will report to the FDA, regardless of the site of occurrence, any serious adverse event that meets the FDA's criteria for expedited reporting following the reporting requirements and timelines set by the FDA.

## 7.5 Expedited Reporting to BMS Worldwide Safety

All Serious Adverse Events (SAEs) that occur following the subject's written consent to participate in the study through 30 days of discontinuation of dosing must be reported to BMS Worldwide Safety.

- The FDA Medwatch form should be used to report SAEs. The BMS protocol ID number must be included on whatever form is submitted by the Sponsor/Investigator.
- Following the subject's written consent to participate in the study, all SAEs, whether related or not related to study drug, are collected, including those thought to be associated with protocol-specified procedures. The investigator should report any SAE occurring after these time periods that is believed to be related to study drug or protocol-specified procedure.

SAEs and pregnancies must be reported to BMS within 24 hours of learning of the event regardless of causality. SAEs must be recorded on BMS or an approved form; pregnancies must be reported on a Pregnancy Surveillance Form.

A **serious AE (SAE)** is any untoward medical occurrence that at any dose:

- a) results in death
- b) is life-threatening (defined as an event in which the subject was at risk of death at the time of the event; it does not refer to an event which hypothetically might have caused death if it were more severe)
- c) requires inpatient hospitalization or causes prolongation of existing hospitalization (see **NOTE** below)
- d) results in persistent or significant disability/incapacity
- e) is a congenital anomaly/birth defect
- f) is an important medical event (defined as a medical event(s) that may not be immediately life-threatening or result in death or hospitalization but, based upon appropriate medical and scientific judgment, may jeopardize the subject or may require intervention [e.g., medical, surgical] to prevent one of the other serious outcomes listed in the definition above.) Examples of such events include, but are not limited to, intensive treatment in an emergency room or at home for allergic bronchospasm; blood dyscrasias or convulsions that do not result in hospitalization.) Potential drug induced liver injury (DILI) is also considered an important medical event. (See Section 6.6 for the definition of potential DILI.)
- g) Suspected transmission of an infectious agent (eg, any organism, virus or infectious particle, pathogenic or non-pathogenic) via the study drug is an SAE.
- h) Although pregnancy, overdose and cancer are not always serious by regulatory definition, these events must be handled as SAEs. (See Section 6.1.1 for reporting pregnancies).

**NOTE:**

The following hospitalizations are not considered SAEs in BMS clinical studies:

- a visit to the emergency room or other hospital department < 24 hours, that does not result in admission (unless considered "important medical event" or event life threatening)
- elective surgery, planned prior to signing consent
- admissions as per protocol for a planned medical/surgical procedure
- routine health assessment requiring admission for baseline/trending of health status (eg, routine colonoscopy)
- medical/surgical admission for purpose other than remedying ill health state and was planned prior to entry into the study. Appropriate documentation is required in these cases admission encountered for another life circumstance that carries no bearing on health status and requires no medical/surgical intervention (eg, lack of housing, economic inadequacy, care-giver respite, family circumstances, administrative).

**SAE Email Address:** [contact]

**SAE [contact]

If only limited information is initially available, follow-up reports are required. (Note: Follow-up SAE reports should include the same investigator term(s) initially reported.)

If an ongoing SAE changes in its intensity or relationship to study drug or if new information becomes available, a follow-up SAE report should be sent within 24 hours to the BMS (or designee) using the same procedure used for transmitting the initial SAE report.

All SAEs should be followed to resolution or stabilization.

## **7.6 Routine AE reporting to BMS**

All treatment emergent AEs (including severity grade, action taken, and outcome) will be communicated to BMS on a quarterly basis.

## **7.7 Expedited Reporting to Hospital Risk Management**

Participating investigators will report to their local Risk Management office any participant safety reports or sentinel events that require reporting according to institutional policy.

## **7.8 Routine Adverse Event Reporting**

[figure not shown]
All Adverse Events **must** be reported in routine study data submissions to the Overall PI on the toxicity case report forms. **AEs reported through expedited processes (e.g., reported to the IRB, FDA, etc.) must also be reported in routine study data submissions.**

## 8. PHARMACEUTICAL INFORMATION

A list of the adverse events and potential risks associated with the investigational agent administered in this study can be found in Section 7.1.

### 8.1 Ulocuplumab

#### 8.1.1 Description

#### **8.1.3 Storage and Stability**

[REDACTED]

[REDACTED]

[REDACTED]

[REDACTED]

[REDACTED]

#### **8.1.4 Compatibility**

[REDACTED]

#### **8.1.5 Handling**

Qualified personnel, familiar with procedures that minimize undue exposure to themselves and the environment, should undertake the preparation, handling, and safe disposal of the chemotherapeutic agent in a self-contained and protective environment.

#### **8.1.6 Availability**

Ulocuplumab is provided as global open label supply, packaged and labeled under the responsibility of Bristol-Myers Squibb Drug Supply Management. Study treatment labels will be in the local language and comply with the legal requirements of each country. They will include storage conditions for the drug but no information about the patient.

#### **8.1.7 Preparation**

[REDACTED]

#### **8.1.8 Administration**

#### **8.1.9 Ordering (BMS to provide)**

In this protocol, investigational product is Ulocuplumab, which will be supplied by BMS, where other preventative medications or SOC medications that are not considered IMP, are not supplied by BMS. Ancillary supplies, such as NSS, syringes, needles, etc will be sourced and supplied locally by the site.

The process for ordering study drug from BMS for the initial shipment and resupply shipments will be managed by the site through completion of a drug shipment request form, which will be provided by BMS.

#### **8.1.10 Accountability**

The investigator, or a responsible party designated by the investigator, should maintain a careful record of the inventory and disposition of the agent using the NCI Drug Accountability Record Form (DARF) or another comparable drug accountability form. (See the NCI Investigator's Handbook for Procedures for Drug Accountability and Storage.)

#### **8.1.11 Destruction and Return**

The Drug Accountability Log will contain the date and amount of study drugs received, and unused vials destroyed. All used and partially used study drug will be destroyed by the site, in accordance with the site's standard operating procedures (SOPs).

[figure not shown]
## 8.2 Ibrutinib

### 8.2.1 Description

Ibrutinib is 1-[(3*R*)-3-[4-amino-3-(4-phenoxyphenyl)-1*H*-pyrazolo[3,4-d]pyrimidin-1-yl]-1-piperidinyl]-2-propen-1-one and has a molecular weight of 440.50 g/mole (anhydrous basis). Ibrutinib exhibited 18% to 23% oral bioavailability in rats and 7% to 11% oral bioavailability in dogs. The mean terminal half-life of ibrutinib after oral administration ranged from 1.7 to 3.1 hours in mice, 1 to 4.7 hours in rats, and 3.3 to 6.4 hours in dogs. Preliminary results suggest a 1.5- to 2.5-hour half-life of ibrutinib in humans. The effects of renal and/or hepatic impairment on drug clearance are not known at this time. In vitro studies have indicated that ibrutinib is metabolized extensively by cytochrome P450 (CYP) 3A4.

### 8.2.2 Form

The structure of ibrutinib is:

Ibrutinib is a white to off-white crystalline solid. Ibrutinib has a single chiral center and is the R-enantiomer. Ibrutinib product is manufactured for Pharmacyclics LLC by a contract manufacturer.

Ibrutinib PO Hard Gelatin Capsule is an oral formulation containing micronized ibrutinib and the following compendial excipients: microcrystalline cellulose (NF); croscarmellose sodium (NF); sodium lauryl sulfate (NF); may contain magnesium stearate (NF). The 140 mg strength contains 140 mg of the active ingredient, ibrutinib, adjusted for water content and purity in a size 0, white, hard gelatin capsule. Capsules are packaged in 60-cc high-density polyethylene (HDPE) bottles with an induction seal and a child resistant screw top cap. Each bottle is distributed by Pharmacyclics LLC. The number of capsules per bottle is indicated on the label.

Ibrutinib is also available in tablets in 140mg, 280mg, and 420mg strengths. Each 140mg tablet is a yellow green to green round tablet debossed with “ibr” on one side and “140” on the other side. Each 280mg tablet is a purple oblong tablet debossed with “ibr” on one side and “280” on the other side. Each 420mg tablet is a yellow green to green oblong tablet debossed with “ibr” on one side and “420” on the other side.

#### 8.2.3 Storage and Stability

Ibrutinib should be stored according to the package insert.

#### 8.2.4 Handling

N/a. Ibrutinib will be commercially supplied.

#### 8.2.5 Availability

Ibrutinib is considered standard of care for this patient population. It will be commercially sourced and charged to patient insurance.

#### 8.2.6 Administration

Ibrutinib should be self-administered daily by the participant according to the package insert.

#### 8.2.7 Ordering

Ibrutinib is commercially available.

#### 8.2.8 Accountability

The investigator or designee will comply with all institutional commercial drug SOPs.

#### 8.2.9 Destruction and Return

N/A.

### **9. BIOMARKER, CORRELATIVE, AND SPECIAL STUDIES**

#### **9.1 Biomarker Studies**

##### **9.1.1 Laboratory Correlative Studies**

Bone marrow aspirate (approximately 45cc) will therefore be collected at the baseline screening visit, on day 1 of cycle 2 (phase I participants only), at the completion of cycle 6 following the last ulocuplumab infusion, at year 1, and thereafter every year until study completion. Bone marrow lymphoplasmacytic cells will be genotyped for MYD88 and CXCR4 at baseline to determine eligibility, and at every BM sampling for the cancer cell fraction of mutated CXCR4 cells determined by next generation (whole exome) sequencing; ii) wild-type and mutated CXCR4 transcriptional signature determined by transcriptome analysis; and iii) CXCR4, CXCR7 cell surface expression, pAKT, and pERK determined by multicolor flow cytometry.

## 10. STUDY CALENDAR

	Screening* ≤ 30 days from study entry	Treatment Phase							Off Treatment Assessment  Within 4 ± 2 weeks of completing or coming off study.	Follow-Up Phase  Post Treatment. Every 12 ± 2 weeks for 24 months, next therapy or death.
		Cycle 1				Cycles 2-6 (+/- 2 days)		Cycles 9,12,15,18,21 ,24,27,30,33, 36,39,42,45		
		Day 1	Day 8 (+/- 2 days)	Day 15 (+/- 2 days)	Day 22 (+/- 2 days)	Day 1 (+/- 2 days)	Day 15 (+/- 2 days)	Day 1 (+/- 14 days)		
Physical exams*  , weight, height	X	X				X		X	X	X
ECOG performance status (see Appendix A)	X	X				X		X	X	X
CT of the chest & abdomen / pelvis 	X					X 		X 	X 	X (if applicable)
Bone marrow biopsy and aspiration 	X					X 		X 	X	X (if applicable)
Serum immuno- electrophoresis	X					X		X	X	X
Serum IgM	X	X	X	X	X	X	X	X	X	X
Serum IgA, IgG	X					X		X	X	X
Complete Blood Count plus differential 	X	X	X	X	X	X	X	X	X	X
Coagulation profile: PT, PTT, PT-INR	X									
Chemistry including: Electrolytes, Renal (BUN, Creatinine) and Hepatic function testing [ALT (SGPT), AST (SGOT), Alk phos, total Bilirubin], albumin, total protein	X	X	X	X	X	X	X	X	X	X
Vital signs (Temp, HR, RR, BP)	X	X**	X**	X**	X**	X**	X**	X		
Beta-2 microglobulin, Von Willebrand	X									
Pregnancy Test 	X									
HBsAg, HBsAb, HbcAB	X									
HCV, HIV Ab	X									
Ulocuplumab administration		X	X	X	X	X	X			
Ibrutinib diary review						X		X		

\* Physical exam, vital signs, laboratory tests, and weight do not need to be repeated if Cycle 1, Day 1 is within 14 days of Screening. Cycle 1, Day 1 labs, if drawn, do not need to re-confirm eligibility prior to administering first dose.

\*\*Vital signs (Blood pressure, heart rate, respiratory rate, temperature) should be taken prior to infusion, every 15 minutes during the infusion ( $\pm$ 5 minutes), and 15, 30, and 60 minutes post infusion ( $\pm$  5 minutes).

 More frequent visits may be required at the discretion of the treating physician.

**If CT scans of the chest, abdomen and pelvis have been collected and done within 90 days of Cycle 1 Day 1 they will not be required at the screening visit. If the participant has known extramedullary disease outside the chest, abdomen, or pelvis, imaging should be performed with investigator-preferred modality.** Scans will be repeated on days 1 of cycle 12, 24, 36, and off-treatment assessment **for participants who had extramedullary disease at baseline (i.e. lymph nodes 15 mm or greater, spleen  $\geq$ 15 cm, or other documented extramedullary site of WM disease).** If participant has disease only outside chest, abdomen, and pelvis, only the affected area will need to be re-imaged with the same modality as at screening. CT scans will also be done at the completion of Cycle 6 on Day 15 (+/- 2 days). Scans will also be repeated to confirm a complete response if the participant has no detectable monoclonal protein and had extramedullary disease (as noted above) at baseline and at the discretion of the investigator.

Bone marrow biopsy and aspiration will be done during the screening visit or within 90 days prior to Cycle 1 Day 1, and on days 1 of cycle 6, 12, 24, 36, and off-treatment assessment. Bone marrow biopsy and aspiration will also be done at the completion of Cycle 6 on Day 15 (+/- 2 days). Up to 45 additional cc of aspirate will be collected (if collectable) at these sampling times for laboratory correlative studies specified in section 9.1.1. A bone marrow aspirate only will be collected on day 1 of cycle 2 for laboratory correlative studies per 9.1.1 from participants on the Phase I part of the study only. Bone marrow biopsy and aspiration may also be performed to confirm complete response, or progression, and study samples may be collected at this time to perform laboratory corollary studies per section 9.1.1

For women of childbearing potential only, a serum pregnancy test is required at screening.

Participants still on commercial ibrutinib as of study termination on 12/31/22 are not required to complete the Off Treatment visit and will not enter follow-up.

All follow-up will be terminated as of 12/31/22.

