## 2.5 Correlative Studies Background

In most WM patients, CXCR4 mutations are subclonal with an estimated median cancer cell fraction of 40-50%, though the transcriptional signature remains relatively homogeneous despite the subclonal nature of CXCR4 mutations in WM (Hunter et al, 2016; Xu et al, 2016). CXCR4 mutated patients also show loss of regulatory genes that regulate MYD88 signaling (Hunter et al, 2016). Furthermore, the presence of CXCR4 WHIM mutations confers enhanced activation of AKT and ERK (Cao et al, 2014; Cao et al, 2015). Bone marrow aspirate (approximately 45cc) will therefore be collected at the baseline screening visit, on day 1 of cycle 2 (phase 1 participants only), at the completion of cycle 6 following the last ulocuplumab infusion, at year 1, and thereafter every year until study completion. Bone marrow lymphoplasmacytic cells will be genotyped for MYD88 and CXCR4 at baseline to determine eligibility, and at every BM sampling for the cancer cell fraction of mutated CXCR4 cells determined by next generation (whole exome) sequencing; ii) wild-type and mutated CXCR4 transcriptional signature determined by transcriptome analysis; and iii) CXCR4, CXCR7 cell surface expression, pAKT, and pERK determined by multicolor flow cytometry.

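### Study Calendar footnote 3 schedules two Cycle 6 marrow procedures where Sections 2.5 and 9.1.1 list one, and it omits the rule that the marrow follows the last ulocuplumab infusion

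*Combined protocol and SAP*

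**What the plan says.** Three places in the combined protocol and SAP set the marrow schedule.

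- **Section 10, Study Calendar, footnote 3.** After the baseline sample, marrow biopsy and aspiration fall "on days 1 of cycle 6, 12, 24, 36, and off-treatment assessment". The next sentence reads: "Bone marrow biopsy and aspiration will also be done at the completion of Cycle 6 on Day 15", with a window of ±2 days. Research material is then attached to all of these times: "Up to 45 additional cc of aspirate will be collected (if collectable) at these sampling times". A separate, optional provision follows: "Bone marrow biopsy and aspiration may also be performed to confirm complete response, or progression".
- **Section 2.5.** After baseline, the research aspirates come "on day 1 of cycle 2 (phase 1 participants only), at the completion of cycle 6 following the last ulocuplumab infusion", then at year 1 and annually.
- **Section 9.1.1.** The schedule is the same: "at the completion of cycle 6 following the last ulocuplumab infusion, at year 1, and thereafter every year until study completion".

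The CT schedule in footnote 2 has a similar structure. Its Day 1 list is "Scans will be repeated on days 1 of cycle 12, 24, 36, and off-treatment assessment", and it adds "CT scans will also be done at the completion of Cycle 6 on Day 15". It has a Cycle 6 Day 15 scan but no Cycle 6 Day 1 scan.

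Sections 5.1 and 5.3.1 give ulocuplumab on Days 1 and 15 of Cycles 2-6, each ±2 days. As the calendar grid reads in the available text, the marrow mark for Cycles 2-6 sits under Day 1 and the Day 15 column is blank.

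**The concern.** A site working from the calendar would do a marrow biopsy and aspiration at the start of Cycle 6 and another about two weeks later. A site working from Section 2.5 or 9.1.1 would do one. The difference is an invasive procedure in patients taking a drug for which Section 7.1.1.2 describes hemorrhagic events.

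The second issue is order. Sections 2.5 and 9.1.1 define the Cycle 6 sample as coming after the last ulocuplumab infusion. Footnote 3 gives only a day and a window, and the infusion has the same day and window. Section 2.2 reports, from the myeloma study, that leukocytes were mobilized into blood 2 hours after ulocuplumab, with only a partial decrease at 3-4 days. So it is plausible, though these documents do not show it, that timing relative to the infusion matters for marrow assays such as the fraction of CXCR4-mutated cells and CXCR4 surface expression.

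**Working it through.** The plan gives no figure to reproduce. The check is a comparison of schedules plus day arithmetic.

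**Step 1: date the Cycle 6 visits.** Cycles are 28 days (Section 5.1), so study day = (cycle − 1) × 28 + day.
- Cycle 6 Day 1: 5 × 28 + 1 = 141.
- Cycle 6 Day 15: 5 × 28 + 15 = 155.
- Gap: 155 − 141 = 14 days. With ±2 days on each visit it runs from 10 to 18 days.

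**Step 2: locate the last infusion.** Four in Cycle 1 plus 2 × 5 in Cycles 2-6 gives 14. The fourteenth is Cycle 6 Day 15, so the Cycle 6 Day 1 marrow always precedes it.

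**Step 3: count fixed-date on-treatment marrows after baseline.** Treatment lasts 47 × 28 = 1316 days, about 3.6 years, so Section 9.1.1 reaches years 1, 2 and 3.

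| Time | Footnote 3 | Section 9.1.1 |
|---|---|---|
| Cycle 2 Day 1 (Phase I only, aspirate) | 1 | 1 |
| Cycle 6 Day 1 | 1 | 0 |
| Cycle 6 Day 15 / completion of Cycle 6 | 1 | 1 |
| Cycles 12, 24, 36 / years 1, 2, 3 | 3 | 3 |
| Total, Phase I | 6 | 5 |
| Total, Phase II | 5 | 4 |

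The difference is the Cycle 6 Day 1 procedure.

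**Step 4: can the lists be reconciled as clinical versus research marrows?** No. Footnote 3 collects the correlative aspirate at every time it lists, including Cycle 6 Day 1. Nor is there a response-assessment reason for a fixed Day 1 marrow: CR, VGPR, PR, MR, SD and PD in Section 11.1.2 are defined by serum IgM, immunofixation, symptoms, adenopathy or spleen, and other extramedullary or transformation events. Marrow to confirm complete response or progression has its own optional sentence.

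**Step 5: compare the windows.** Marrow and last infusion can each fall on Days 13-17. From footnote 3 alone, the marrow could come up to 17 − 13 = 4 days before the infusion or up to 4 days after it. With the order in Section 9.1.1 applied, the range is 0 to 4 days after.

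**The case against.** The strongest reply is that Section 9.1.1 is a loose description, so a mismatch with it is weak evidence of a mistake. By study day, Day 1 of Cycles 12, 24 and 36 falls on 309, 645 and 981. Anniversaries at about 365, 730 and 1095 are 56, 85 and 114 days later, beyond the ±14-day visit window. Section 9.1.1 also omits off-treatment and confirmatory marrows, and it runs its assays at every marrow sampling. The Day 1 sample therefore has a general correlative purpose, and marrow and CT need not follow the same dates.

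That stands against one inference a reader might draw, that Cycle 6 Day 1 is a drafting leftover. The documents do not establish that. It does not remove the conflict in the number of Cycle 6 procedures.

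On order, footnote 3 cites Section 9.1.1, which states the sequence, and the calendar has a single Day 15 column for Cycles 2-6. A reader might infer that the last sample would often precede the last dose. The documents do not support that: a Day 13 marrow with a Day 17 infusion needs two attendances and disregard of Section 9.1.1. What remains is that the footnote does not carry the order over, including for two procedures done at one visit.

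A reader might also try to put a bleeding risk on the extra procedure. Section 2.3 reports one discontinuation for hematoma after marrow biopsy among 63 ibrutinib patients, but not how many biopsies they had. No per-procedure rate follows.

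**Conclusion.** The point holds as a minor inconsistency with a patient-burden consequence. Footnote 3, followed literally, adds one marrow biopsy and aspiration per participant in Cycle 6, with up to 45 cc of research aspirate if collectable, nominally 14 days before another. The missing sequence is a smaller matter, because Section 9.1.1 supplies it.

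This rests on reading *also* in footnote 3 as additional, which is its ordinary meaning, and on the grid marks standing where the extracted text places them.

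It would be wrong to infer that any trial result is compromised. The primary response endpoint does not use marrow, and DLT rules, MTD and sample size do not depend on it. Phase II never opened, all enrolled participants completed ulocuplumab, and follow-up ended on 12/31/22, so no current participant is affected. The value of correcting the text lies in a consistent record and in any reuse of the schedule.

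**What to change.** In footnote 3:

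1. Delete 6 from the Day 1 list, leaving Cycles 12, 24, 36 and the off-treatment assessment.
2. State that one Cycle 6 marrow is done, after the Cycle 6 Day 15 ulocuplumab infusion, within a narrow fixed window, for example at the same visit or within 2 days after.

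In the grid, move the Cycle 6 marrow mark to the Day 15 column of Cycles 2-6, keeping the Day 1 mark only for the Phase I Cycle 2 aspirate.

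If the Cycle 6 Day 1 marrow was intended, keep it and add it to Sections 2.5 and 9.1.1 with its purpose.

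The window should stay narrow. Allowing the marrow at any time before Cycle 7 Day 1 would permit up to 28 − 13 = 15 days after infusion, against 0 to 4 days now under the order in Section 9.1.1. Given the mobilization data in Section 2.2, that could mix unlike samples at one timepoint. The suggested window gives 0 to 2 days.

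The cost is two wording edits and one grid edit. No visit is added if the marrow follows the infusion the same day; a later day would add one. The loss is one correlative sample per participant taken before the last infusion, for which Section 13 specifies no analysis.
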